8.6 Unblinding Procedures

All patients will receive stimulation and unblinding will not play a role in this study.

8.7 Stopping Rules

Study safety will be monitored by the co-PIs .The study will be stopped at if the following endpoints are reached:

1. If recruitment for the study is not feasible
 - a. no recruitment after 1 year
 - b. > 4 drop outs due to any reason (80% feasibility)
2. If TMS is deemed unsafe to patients with epilepsy

- a. > 3 patients with increase in baseline seizure frequency
- b. > 3 patients with significant worsening of depression
- c. > 3 patients with significant side effects of TMS other than seizures

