1.5 Dose Rationale and Risk/Benefits

Low-frequency (LF) TMS refers to TMS delivered at a frequency of 1 Hz or below. Unlike HF TMS, LF TMS can decrease cortical excitability and may have anticonvulsant effects[42]. Low frequency TMS applied to right DLPFC also has an extensive though smaller database supporting its antidepressant efficacy, and comparisons to left HF DLPFC TMS suggest both treatments work equally as well[43, 44]. Surprisingly, LF TMS has not been investigated as an antidepressant treatment in patients with epilepsy, though it would have clear advantages compared to HF TMS including increased tolerability and potentially anticonvulsant effects.

2 Study Objectives

Specific Aim 1: To examine the safety and feasibility of accelerated low-frequency transcranial magnetic stimulation (TMS) to the right dorsolateral prefrontal cortex in patients with epilepsy and comorbid depression.

Hypothesis 1.a. (safety): Treatment will not produce serious adverse events defined as an increase in seizure rate or hospitalization.

Hypothesis 1.b. (safety): Treatment will not be associated with a higher rate of adverse events as measured by a modified Systematic Assessment for Treatment Emergent Events (SAFTEE) given at baseline and immediately post-TMS.

Hypothesis 1.c. (feasibility): At least 80% of participants will complete the study protocol.

Specific Aim 2: To examine the utility of electrophysiological and behavioral profiles as biomarkers of depression correlated with response to treatment with right-DLPFC TMS in patients with epilepsy.

Hypothesis 2a: Changes in dense array EEG based biomarkers of depression (hemispheric frontal alpha power asymmetry, anterior cingulate theta power, and frontotemporal alpha coherence) will correlate with changes in depression scores.

3 Study Design

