7.1 Statistical Methods

The study will be closely monitored for safety parameters with stopping rules as defined in Section 8.7. At the conclusion of the study, baseline demographics and clinical characteristics will be summarized with means, proportions and associated standard deviations. For safety, occurrence rates of SAE (seizures or hospitalizations) will be estimated and exact binomial confidence intervals will be formed. Very few if any are expected in this small study. The SAFTEE scale will be compared before and after TMS with independent t-tests based on the individual changes from baseline. The study completion rates will be estimated and compared to the target rate of 80% using exact tests for binomial data.

The secondary outcomes will be measured before and after treatment using dense-array EEG biomarkers and depression scores along with test results during functional MRI and EEG. Paired t-tests will be used to compare *change* in depression severity, memory, executive functioning, quality of life, and social cognition from baseline to endpoint. MRI patterns of activation will be analyzed. Analysis of variance for repeated measures will be used to test task and neuropsychological testing results.

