8.5.1 Investigator reporting: notifying the Dartmouth IRB

This section describes the requirements for safety reporting by investigators who are Dartmouth faculty, affiliated with a Dartmouth research site, or otherwise responsible for safety reporting to the Dartmouth IRB. The Dartmouth College IRB (CPHS) requires expedited reporting of those events related to study participation that are unforeseen and indicate that participants or others are at increased risk of harm. The Dartmouth IRB will not acknowledge safety reports or bulk adverse event submissions that do not meet the criteria outlined below. The Dartmouth IRB requires researchers to submit reports of the following problems within 10 working days from the time the investigator becomes aware of the event:

- Any adverse event (regardless of whether the event is serious or non-serious, on-site or off-site) that occurs any time during or after the research study, which in the opinion of the principal investigator is:

Unexpected (An event is “unexpected” when its specificity and severity are not accurately reflected in the protocol-related documents, such as the IRB-approved research protocol, any applicable investigator brochure, and the current IRB-approved informed consent document and other relevant sources of information, such as product labeling and package inserts.)

AND

Related to the research procedures (An event is “related to the research procedures” if in the opinion of the principal investigator or sponsor, the event was more likely than not to be caused by the research procedures.)

Reporting Process

Unanticipated problems posing risks to subjects or others as noted above will be reported to the Dartmouth IRB using the form: “Unanticipated Problems Posing Risks to Subjects or Others Including Reportable Adverse Events” or as a written report of the event (including a description of the event with information regarding its fulfillment of the above criteria, follow-up/resolution and need for revision to consent form and/or other study documentation).

Copies of each report and documentation of IRB notification and receipt will be kept in the Clinical Investigator’s study file.

Reporting Deaths: more rapid reporting requirements

Concerning deaths that occur during the course of a research study, the following describes the more rapid reporting requirement of the Dartmouth IRB for specific situations:

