- Report the event within 24 hours when the death is unforeseen (unexpected) and indicates participants or others are at increased risk of harm.
- Report the event within 72 hours, for all other deaths, regardless of whether the death is related to study participation.

For reportable deaths, the initial submission to the Dartmouth IRB may be made by contacting the IRB Director or Associate Director. The AE/Unanticipated Problem Form is required as a follow up to the initial submission.

Other Reportable events:

For clinical drug trials, the following events are also reportable to the Dartmouth IRB:

- Any adverse experience that, even without detailed analysis, represents a serious unexpected adverse event that is rare in the absence of drug exposure (such as agranulocytosis, hepatic necrosis, Stevens-Johnson syndrome).
- Any adverse event that would cause the sponsor to modify the investigators brochure, protocol or informed consent form, or would prompt other action by the IRB to assure protection of human subjects.
- Information that indicates a change to the risks or potential benefits of the research, in terms of severity or frequency. For example:
 - An interim analysis indicates that participants have a lower rate of response to treatment than initially expected.
 - Safety monitoring indicates that a particular side effect is more severe, or more frequent than initially expected.
 - A paper is published from another study that shows that an arm of your research study is of no therapeutic value.
- Change in FDA safety labeling or withdrawal from marketing of a drug, device, or biologic used in a research protocol.
- Breach of confidentiality
- Change to the protocol taken without prior IRB review to eliminate apparent immediate hazard to a research participant.
- Incarceration of a participant when the research was not previously approved under Subpart C and the investigator believes it is in the best interest of the subject to remain on the study.
- Complaint of a participant when the complaint indicates unexpected risks or the complaint cannot be resolved by the research team.
- Protocol violation (meaning an accidental or unintentional deviation from the IRB approved protocol) that in the opinion of the investigator placed one or more participants at increased risk, or affects the rights or welfare of subjects.

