8.8 Medical Monitoring

It is the responsibility of the Principal Investigator to oversee the safety of the study at his/her site. This safety monitoring will include careful assessment and appropriate reporting of adverse events as noted above, as well as the construction and implementation of a site data and safety-monitoring plan. Medical monitoring will include a regular assessment of the number and type of serious adverse events.

9 Data Handling and Record Keeping

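### As supplied, Section 8.7 stops the study on patient counts only, so a single TMS-related death, suicide attempt, unplanned hospitalization or atypical seizure requires no pause in new TMS starts.

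*Combined protocol and SAP*

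**What the plan says.** Section 7.1 states: "The study will be closely monitored for safety parameters with stopping rules as defined in Section 8.7". Section 8.7 names the co-PIs as monitors and lists three safety endpoints. Each is reached when more than 3 patients have, respectively, a rise in baseline seizure frequency (2a), a significant worsening of depression (2b), or other significant side effects (2c: "> 3 patients with significant side effects of TMS other than seizures"). Item 1b, under recruitment feasibility, stops the study after more than 4 drop-outs for any reason. No item names death, suicide attempt or hospitalization, and no safety item acts on one event. Yet Hypothesis 1.a in Section 2 makes hospitalization part of the primary safety question: "Treatment will not produce serious adverse events defined as an increase in seizure rate or hospitalization".

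Single events are handled elsewhere, at two levels.

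- **Affected patient.** Under 4.2.1, one atypical seizure ends that patient's treatment. Under 8.2, a QIDS item 12 answer of 2 or 3 leads to the C-SSRS, notice to the study psychiatrist and a REDCap entry, and treatment may be changed. Under 8.3, a seizure during TMS halts that patient's treatment until the neurologist decides.
- **Study.** Section 8.5.1 tells investigators to "submit reports of the following problems within 10 working days from the time the investigator becomes aware of the event", for adverse events that are unexpected and related, where related means that "the event was more likely than not to be caused by the research procedures". Deaths go faster: 24 hours if unforeseen and indicating increased risk, otherwise "Report the event within 72 hours, for all other deaths, regardless of whether the death is related to study participation". Section 8.8 adds: "Medical monitoring will include a regular assessment of the number and type of serious adverse events". It also calls for "the construction and implementation of a site data and safety-monitoring plan", and Section 13 lists a study monitoring plan as Attachment E. Neither plan is in the supplied text.

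**The concern.** A count rule suits events that are expected at some background rate, such as typical seizures in people with epilepsy. It does not suit events for which one case should prompt a look before anyone else is treated. Section 1.4 says that low-frequency TMS has not been evaluated as an antidepressant in this population, and 5.1 gives the whole course over three to four days. Under 8.7, one related death or suicide attempt would be at most the first of four patients needed in a category.

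The atypical seizure is the sharper case. Section 4.2.1 treats it as serious enough to end a patient's treatment. But 2c leaves out seizures, and one long or unusually severe seizure need not raise that patient's seizure frequency under 2a. If the patient is withdrawn, the event may register only as one drop-out under 1b.

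What is at stake is whether the next patient starts TMS before such an event has been reviewed. Under the supplied text the co-PIs decide that at their discretion.

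**Working it through.** Section 8.7 gives no error rate or operating characteristic, so there is no figure of the plan's to reproduce. The check has two parts.

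**1. Is a hold required anywhere?** Taking the responses side by side:

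- 4.2.1, 8.2 and 8.3 act on the affected patient.
- 8.5.1 requires reports to the IRB. A report may lead to a pause, but the section does not impose one. A non-fatal event that is only possibly related falls short of its causality standard.
- 8.8 requires regular SAE assessment, with no trigger, deadline or action.
- 8.7 acts at 4 or more patients per safety category.

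No supplied section requires new starts to wait after one event.

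**2. How large is the exposure?**

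Inputs from the documents:
- 20 patients, all treated (5.2).
- Study dates 11/1/2015 to 10/31/2020 (Study Summary), which is 60 months.
- Last follow-up at 6 months (6.10).
- Course of at most four days (5.1).
- Reporting limits of 10 working days (14 calendar days), 24 hours and 72 hours (8.5.1).

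Assumptions:
- Starts occur at random, with exponential gaps.
- The per-patient rate p of a qualifying event is 0.01, 0.05 or 0.10. The documents give no such rate. Section 7.2 uses 0.05 and 0.10 as scenarios for all SAEs, which is a different set of events.

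Average gap between starts: (60 − 6) / 20 = 2.7 months, or 82.2 days.

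Chance that another patient starts within t days of an event = 1 − exp(−t / 82.2):
- Non-fatal event, t = 14: 1 − exp(−14/82.2) = 0.157
- Death, t = 1: 1 − exp(−1/82.2) = 0.012
- Death, t = 3: 1 − exp(−3/82.2) = 0.036

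Sensitivity of the 14-day figure to faster enrolment (no section supports these paces):
- 27 months, gap 41.1 days: 1 − exp(−14/41.1) = 0.289
- 12 months, gap 18.3 days: 1 − exp(−14/18.3) = 0.535

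Expected qualifying events, and so expected pauses, = 20p: 0.2, 1.0 and 2.0.

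Expected events followed by another start within 14 days = 20p × 0.157:
- p = 0.01: 0.2 × 0.157 = 0.03
- p = 0.05: 1.0 × 0.157 = 0.16
- p = 0.10: 2.0 × 0.157 = 0.31

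These products are slightly high, because no start can follow an event that occurs after the last patient has begun.

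**The case against.** The strongest reply is that the plan may already contain the hold. Attachment E and the 8.8 site plan are its natural home, and neither was supplied. This stands: the finding is about the supplied text, and a reader should not infer that the trial has no single-event hold.

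Second, the practical gain is small. The co-PIs already monitor safety, a psychiatrist supervises treatment, and a neurologist is on call. At the planned pace the next start is usually weeks away. The reporting deadline is also an outer limit, not the time the co-PIs need to react. This stands too, and it sets the size of the point. The pause adds a required, documented decision by the same people, not independent oversight. What remains is that discretion is not a requirement, and writing the requirement down costs little.

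A reader might also infer that a whole TMS course could be given before any of these events is reported. That can happen within 10 working days for a non-fatal event. It does not fit the 24-hour limit for a death, and a three-day course at most just fits 72 hours.

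Finally, a reader might take the chance that a 4-of-20 rule fires (0.016 at a rate of 0.05, 0.133 at 0.10) as the chance that harm is caught. That is not supported. Those rates are the Section 7.2 scenarios for all SAEs, the events here are a narrower set, and the count rules were not written for single sentinel events.

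**Conclusion.** The point holds for the supplied text, as a cheap improvement to a design choice. Followed as written, 8.7 lets new TMS starts continue after one related death, suicide attempt, unplanned hospitalization or atypical seizure, and the last of these may count under no safety item.

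The benefit is a modest safeguard, worth most if starts cluster. Its size rests on even average enrolment over 54 months, randomly timed starts and assumed event rates. Confidence is medium, because the two monitoring plans have not been seen.

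**What to change.** Add one sentence to 8.7 and keep the existing counts:

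> Any death, suicide attempt, unplanned hospitalization (including hospitalization for a seizure), or atypical seizure meeting 4.2.1, judged at least possibly related to TMS, whenever the study team learns of it, pauses new TMS starts until the co-PIs document an event review and decide whether to continue; typical seizures without hospitalization stay under 2a and 4.2.1.

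Three phrases do specific work:
- Naming hospitalization for a seizure settles whether it counts. Section 8.1 exempts some admissions for the target disease from adverse event reporting.
- The words on when the team learns of the event are needed because 8.1 narrows adverse event reporting after 30 days to seizure frequency and depression.
- The threshold of at least possibly related is wider than the causality standard in 8.5.1, so the pause does not depend on whether an IRB report is due.

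If Attachment E or the 8.8 site plan already contains such a pause, cite it in 8.7 instead.

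The cost is an occasional short delay to the next start: 20p expected pauses, or 0.2 to 2 at assumed rates of 0.01 to 0.10, where p must include atypical seizures and is not given in the documents. No new committee is needed, and the sample size and analysis do not change.

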8.8 Medical Monitoring

It is the responsibility of the Principal Investigator to oversee the safety of the study at his/her site. This safety monitoring will include careful assessment and appropriate reporting of adverse events as noted above, as well as the construction and implementation of a site data and safety-monitoring plan. Medical monitoring will include a regular assessment of the number and type of serious adverse events.

9 Data Handling and Record Keeping

9.1 Confidentiality

Information about study subjects will be kept confidential and managed according to the requirements of the Health Insurance Portability and Accountability Act of 1996 (HIPAA). Those regulations require a signed subject authorization informing the subject of the following:

- What protected health information (PHI) will be collected from subjects in this study
- Who will have access to that information and why
- Who will use or disclose that information
- The rights of a research subject to revoke their authorization for use of their PHI.

In the event that a subject revokes authorization to collect or use PHI, the investigator, by regulation, retains the ability to use all information collected prior to the revocation of subject authorization. For subjects that have revoked authorization to collect or use PHI, attempts should be made to obtain permission to collect at least vital status (i.e. that the subject is alive) at the end of their scheduled study period.

9.2 Source Documents

Source data and original records will be maintained by the research coordinator at Dartmouth-Hitchcock Medical Center. All source data will be stored in a locked cabinet or office. Demographics and outcome data of participants in the study will be manipulated and stored on a secure, web-based application called REDcap and/or shared drive used for the Department of Neurology's research purposes and managed by the Information Technology Department at Dartmouth-Hitchcock Medical Center. The department follows industry standard procedures for securing the computers, servers, and networks physically and electronically. REDcap will be used as an electronic case report form. Participants will be assigned a random generated number and any identifying information or PHI will be removed prior to analysis.

9.3 Retention

Electronic data will be stored indefinitely. The physical forms and paper data will be kept for three years after completion of the trial.

10 Ethical Considerations

This study is to be conducted according to US and international standards of Good Clinical Practice (FDA Title 21 part 312 and International Conference on Harmonization guidelines), applicable government regulations and Institutional research policies and procedures.

This protocol and any amendments will be submitted to a properly constituted independent Ethics Committee (EC) or Institutional Review Board (IRB), in agreement with local legal prescriptions, for formal approval of the study conduct. The decision of the EC/IRB concerning the conduct of the study will be made in writing to the investigator and a copy of this decision will be provided to the sponsor before commencement of this study. The investigator should provide a list of EC/IRB members and their affiliate to the sponsor.

All subjects for this study will be provided a consent form describing this study and providing sufficient information for subjects to make an informed decision about their participation in this study. See Attachment A for a copy of the Subject Informed Consent Form. The consent form will be submitted with the protocol for review and approval by the EC/IRB for the study. The formal consent of a subject, using the EC/IRB-approved consent form, must be obtained before that subject undergoes any study procedure. The consent form must be signed by the subject or legally acceptable surrogate, and the investigator-designated research professional obtaining the consent.

11 Study Finances

11.1 Funding Source

This study is financed through a grant from the Diamond Interdisciplinary Neuroscience Grant.

11.2 Conflict of Interest

Any investigator who has a conflict of interest with this study (patent ownership, royalties, or financial gain greater than the minimum allowable by their institution, etc.) must have the conflict reviewed by a properly constituted Conflict of Interest Committee with a Committee-sanctioned conflict management plan that has been reviewed and approved by the study sponsor prior to participation in this study. All Dartmouth investigators will follow the Dartmouth conflict of interest policy.

